##### **5.4.2.1. Binary Endpoints**

All binary endpoints defined using HBsAg values/changes from baseline (HBsAg cut-offs, HBsAg seroclearance/seroconversion, Functional Cure) will be analyzed also using the virtual control approach described in Section 5.3.6.

For single arm point and 90% CI estimates, the Clopper Pearson method will be used. For the difference between paired matched case-control binomial proportions, the McNemar test at 0.05 one-sided Type 1 error rate will be used.

Graphical displays using bar charts and/or radar plots will show the binary endpoints over time, by subgroups of interest, or combining multiple binary endpoints together.

Potential association between treatment outcome and baseline factors will be explored by multivariate logistic regression model in a similar fashion as described in Section 5.3.5.

##### **5.4.2.1.1. LOCF Imputation Method**

- If the lab value at FU Week 12 is missing, the LOCF in conjunction with the next available observation imputation approach will be used. The available non-missing lab test closest to FU Week 12 which is no earlier than FU Week 4 and no later than FU Week 24 will be imputed. If the non-missing lab value before and after the specific timepoint fall equidistant from the target timepoint, the later one will be used to impute the missing value.
- If the lab value at FU Week 24 is missing, the LOCF in conjunction with the next available observation imputation approach will be used. The available non-missing lab test closest to FU Week 24 which is no earlier/later than 12 weeks from the actual time point of interest (FU Week 12 and FU Week 36, respectively) will be imputed.
- If the lab value at FU Week 36 is missing, the LOCF in conjunction with the next available observation imputation approach will be used. The available non-missing lab test closest to

FU Week 36 which is no earlier/later than 12 weeks from the actual time point of interest (FU Week 24 and FU Week 48, respectively) will be imputed.

- If the lab value at FU Week 48 is missing, the LOCF approach will be used with the condition that no value earlier than FU Week 36 may be carried forward.

#### **5.4.2.1.2. NA Treatment Completion Criteria at Week 24 and During FU**

The count and proportion of participants (and associated 90% CI) who met the NA treatment completion criteria at Week 24, will be summarized by intervention arm.

Starting at the end of treatment period, the incidence of participants who did not meet the NA treatment completion criteria will be summarized at each timepoint during the study by intervention arm, accompanied by the distribution of each of the 4 criteria that is not met. The NA treatment completion criteria are based on a threshold for the laboratory tests of ALT, HBV DNA, HBeAg and HBsAg.

The count and proportion of participants (and associated 90% confidence interval) who met the NA treatment completion criteria (Section 5.4.1.1.1) at any time during the FU phase will be summarized by intervention arm. All the NA treatment completion criteria will be checked based on clinical laboratory tests in FU phase.

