All participants will receive the last dose of JNJ-3989 at Week 24 and the last dose of PegIFN- α 2a at Week 23 (Arms 1 and 2) or Week 11 (Arm 3). They will start the FU Period after the Week 24 visit. If the protocol-defined NA treatment completion criteria (described in Section 6.5.1, NA Treatment Completion) are met based on the Week 24 results, treatment with NA will be stopped at the next scheduled visit (ie, FU Week 2), otherwise NA treatment will continue during the complete FU Period. **Note:** Participants who are close to meeting the protocol-defined NA treatment completion criteria with the Week 24 results, and do meet the criteria based on the FU Week 2 results may be allowed to stop NA at FU Week 4, after consultation with the Sponsor.

The NA treatment completion criteria which take ALT, HBV DNA, HBeAg, and HBsAg levels into consideration, have been selected to ensure that only participants with a higher chance of achieving sustained off-treatment response are allowed to stop all study intervention. Across a range of studies, HBsAg levels at end of treatment below 100 IU/mL were consistently associated with favorable off-treatment response (Jeng 2018; Papatheodoridis 2018).

Participants will be monitored closely during the 48-week FU Period and participants who completed NA treatment should re-start NA treatment if NA re-treatment criteria are met (see Section 6.5.2, NA Re-treatment Criteria During Follow-up, for more details).

Follow-up Procedures and Criteria for Re-initiation of NA Treatment

To ensure safety of patients during the FU Period, an ALT flare management plan is in place, including weekly visits for patients with ALT/AST $\geq 3x$ ULN and $\geq 3x$ nadir (ie, lowest value during study participation) until stabilization.

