5.1. Inclusion Criteria

Each potential participant must satisfy all of the following criteria to be enrolled in the study:

A01 (adapted from M01) Adult male or female participants ≥ 18 (or the legal age of consent in the jurisdiction in which the study is taking place) to 65 years of age, inclusive.

M02 Participants must be medically stable based on physical examination, medical history, vital signs, and 12-lead ECG performed at screening. If there are abnormalities, they must be consistent with the underlying illness in the study population. This determination must be recorded in the participant's source documents and initialed by the investigator.

A03 (adapted from M03a) Participants must have chronic HBV infection. HBV infection must be documented by serum HBsAg positivity at screening. In addition, chronicity must be documented by any of the following, at least 6 months prior to screening: serum HBsAg positivity, HBeAg positivity or HBV DNA positivity, ALT elevation above ULN without another cause than HBV infection, documented transmission event. If none of the above are available, the following ways of documenting chronicity are acceptable at the time of screening: liver biopsy with changes consistent with chronic HBV, or absence of marker for acute HBV infection such as positive immunoglobulin M (IgM) anti-hepatitis B surface (HBs) and anti-HBc antibodies.

Participants should:

- be HBeAg-negative, AND
- be anti-HBe antibody-positive, AND
- be on stable HBV treatment, defined as currently receiving NA treatment for at least 2 years prior to screening, and having been on the same NA treatment regimen (at the same dose) as used in this study for at least 3 months at the time of screening, AND
- have documented serum HBV DNA < 60 IU/mL on 2 sequential measurements at least 6 months apart (one of which is at screening), AND
- have documented ALT values $< 2.0 \times$ ULN on 2 sequential measurements at least 6 months apart (one of which is at screening).

M04 Participants must have a body mass index (BMI; weight in kg divided by the square of height in meters) between 18.0 and 35.0 kg/m², extremes included.

A05 (adapted from M05)	Participants must sign a Master ICF (specific for the Master Protocol PLATFORMPAHPB2001) and must sign the ICF specific for this intervention cohort, indicating that he or she understands the purpose of, and procedures required for, the study and is willing to participate in the study.

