A13	
Criterion modified per Amendment 1
 
A13.1 Participants must have serum HBsAg >5 IU/mL at screening, as assessed by quantitative HBsAg assay.

A14	
Participants must have:
 
 a. Fibroscan liver stiffness measurement \leq9.0 kPa within 6 months prior to screening or at the time of screening, OR b. If a Fibroscan result is not available: a liver biopsy result classified as Metavir F0-F2 within 1 year prior to screening. 
Note: Other radiologic liver staging modalities (eg, acoustic radiation force impulse) might be used if standard practice at the site or if otherwise validated and agreed with the Sponsor. Results should be equivalent to Metavir F0-F2.
 
Note: Conventional imaging procedures (eg, conventional liver ultrasound, computed tomography [CT] or magnetic resonance imaging [MRI]) and serum marker panels are not allowed to rule out severe fibrosis or cirrhosis.

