6.5.1. NA Treatment Completion

All participants will receive the last dose of JNJ-3989 at Week 24 and the last dose of PegIFN- α 2a at Week 23 (Arms 1 and 2) or Week 11 (Arm 3). They will start the FU Period after the Week 24 visit. If all of the following NA treatment completion criteria are met based on the Week 24 results, treatment with NA will be stopped at the next scheduled visit (ie, FU Week 2):

- The participant has ALT <3x ULN, AND
- The participant has HBV DNA <60 IU/mL at Week 24 and HBV DNA <LLOQ at the previous visit, or HBV DNA <LLOQ at Week 24, AND
- The participant is HBeAg-negative, AND
- The participant has HBsAg <100 IU/mL.

Note: Participants who are close to meeting the protocol-defined NA treatment completion criteria with the Week 24 results, and do meet the criteria based on the FU Week 2 results may be allowed to stop NA at FU Week 4, after consultation with the Sponsor. In case of ALT elevation \geq 3x ULN at Week 24, the investigator must consider different potential causes of increased ALT to ensure appropriate work up and management as needed. If the ALT elevation is unrelated to HBV activity and/or <3x ULN by FU Week 2, NA completion may be considered at the discretion of the investigator and in consultation with the sponsor.

Participants who do not meet the above criteria based on the Week 24 or FU Week 2 results should continue NA treatment during the 48-week FU Period.

Participants who meet the above-mentioned NA treatment completion criteria will be monitored closely during the 48-week FU Period with a study visit at least once every 4 weeks. NA treatment should be re-started in accordance with the NA re-treatment criteria (see Section [6.5.2](#), NA Re-treatment Criteria During Follow-up, for more details).

The investigator should consider to re-start NA treatment per local standard of care at the EOS visit (Follow-up Week 48) for participants who met the NA treatment completion criteria based on the Week 24 (or FU Week 2) results, who did not re-start NA treatment during the follow-up phase, and who did not achieve and maintain HBsAg seroclearance. NA will not be provided by the sponsor after the final study visit.

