## **5.4.1.3. Time to Event Endpoints**

### **5.4.1.3.1. Time to First HBsAg Seroclearance**

Time to HBsAg seroclearance is defined as the number of days between the date of first study intervention intake and the date of the first occurrence of HBsAg seroclearance (i.e. the date of the first HBsAg seroclearance – the date of first study intervention intake + 1). The participants who withdrew early from the study before achieving HBsAg seroclearance or who did not achieve HBsAg seroclearance will be censored at the last available HBsAg assessment.

Time to HBsAg seroclearance will be also analyzed considering the participants who were retreated with NA before achieving HBsAg seroclearance as censored at the date of NA retreatment.

In addition, time to the first occurrence of the following events (i.e. the date of the first occurrence of the event – the date of first study intervention intake + 1) will be analyzed:

- HBsAg <100 IU/mL
- HBsAg decline  $\geq 1.0 \log_{10}$  IU/mL
- HBsAg decline  $\geq 2.0 \log_{10}$  IU/mL
- HBsAg decline  $\geq 3.0 \log_{10}$  IU/mL

Time to the first occurrence of the events above will be also analyzed considering the participants who were retreated with NA before achieving the event as censored at the date of NA retreatment.

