##### **5.5.1.3.2. Time to First HBcrAg Undetectability**

Time to first undetectability of HBcrAg is defined as the duration from the date of first study intervention intake to the date of the first occurrence of undetectability of HBcrAg (i.e. the date of the first occurrence of HBcrAg<LLOQ – the date of first study intervention intake + 1). The participants who did not achieve undetectability or who early withdrew from the study before achieving undetectability of HBcrAg will be censored at the last HBcrAg assessment before the date of withdrawal.

Time to first undetectability of HBcrAg will be also analyzed considering the participants who were retreated with NA before achieving HBcrAg<LLOQ as censored at the date of NA retreatment.

Only the participants with HBcrAg values  $\geq \text{LLOQ} + 0.5 \log_{10} \text{ U/mL}$  (i.e.  $\geq 3.5 \log_{10} \text{ U/mL}$ ) at baseline will be included in this analysis.

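### Entrants with HBsAg below 100 IU/mL can meet all four NA completion criteria before dosing, yet the completion-rate summary and time to HBsAg <100 set no baseline restriction

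*SAP*

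**What the plan says.** **Entry (Protocol 5.1).** Criterion A13.1 reads "Participants must have serum HBsAg >5 IU/mL at screening". Criterion A03 requires participants to "be HBeAg-negative, AND" to have HBV DNA <60 IU/mL and ALT <2x ULN, each on two measurements. The amendment summary records that the HBsAg limit was lowered from 100 to 5 IU/mL and that the completion criteria were added in the same amendment.

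**Completion criteria (Protocol 6.5.1; SAP 5.4.1.1.1).** These are ALT <3x ULN; HBV DNA <LLOQ at Week 24, or <60 IU/mL with the previous visit <LLOQ; HBeAg-negative; and "The participant has HBsAg <100 IU/mL". The HBsAg criterion is an absolute level, with no decline from baseline required. SAP Table 5 sets the HBV DNA LLOQ at 20 IU/mL.

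**Use as an endpoint.** The proportion meeting these criteria is the only endpoint listed under the secondary objective on efficacy at the end of the 24-week treatment period. SAP 5.4.2.1.2 gives the count and proportion of participants "who met the NA treatment completion criteria at Week 24, will be summarized by intervention arm". The further summaries there start at the end of treatment, so no baseline rate is shown.

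**Time to event.** Beyond seroclearance, SAP 5.4.1.3.1 analyses "time to the first occurrence of the following events", and HBsAg <100 IU/mL heads the list. Time runs from first intake, with no condition on the baseline level. By contrast, SAP 5.5.1.3.2 begins its eligibility rule with "Only the participants with HBcrAg values" and requires a baseline value at least 0.5 log10 above the LLOQ. HBV RNA (5.5.1.3.1) has a similar rule, and ALT normalization (5.4.2.1.11) is limited to participants elevated at baseline.

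**The concern.** An endpoint meant to show what 24 weeks of treatment achieved should be one that participants have still to reach when they start. Here HBsAg is the main criterion left for treatment to achieve, and since Amendment 1 some participants have already achieved it at entry. They raise the completion rate in every arm whatever the drugs do.

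The same participants go on to the off-treatment endpoints at FU Weeks 24 and 48. Protocol 4.2 states that "HBsAg levels at end of treatment below 100 IU/mL were consistently associated with favorable off-treatment response". For someone who entered below 100 IU/mL, a good off-NA course is therefore hard to credit to the study drugs.

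For time to HBsAg <100, the event falls on Day 1 if the pre-dose sample counts. If it does not, the event falls at the first post-baseline visit. That visit is Week 2 in Arms 1 and 3 but Week 4 in Arm 2, because the Schedule of Activities applies the Week 2 visit only to Arms 1 and 3. The log-rank comparison in SAP 5.4.2.3 would then pick up a difference in visit schedule.

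**Working it through.** **1. The plan's own figures.** The documents give no figure for the completion endpoint. Their sizing figures concern the primary endpoint, and they reproduce:
- Exact test, n = 30, 2% versus 32%: reject at 3 or more responders, power 99.9% at one-sided 0.05. At 0.05/3, reject at 4 or more, power 99.5%. The plan states >95%.
- 30/(1 − 0.10) = 33.3, rounded up to 34 per arm, 102 in total.
- Simulated pairwise Hochberg power at 30 per arm, 50% versus 80%: 67 to 68%. The plan states about 68%.

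**2. Entry set against completion.**

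| Marker | Entry | Completion | Secured by entry? |
|---|---|---|---|
| HBeAg | negative | negative | yes |
| ALT | <2x ULN | <3x ULN | yes |
| HBV DNA | <60 IU/mL | <20 IU/mL, or <60 after a value <20 | not if 20–59 IU/mL without a previous value <20 |
| HBsAg | >5 IU/mL | <100 IU/mL | if baseline is below 100 |

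An entrant at 6, 50 or 99 IU/mL needs no HBsAg decline. One at 1,000 needs 1 log10 and one at 10,000 needs 2 log10.

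**3. Inflation of the per-arm rate.** Let f be the share below 100 IU/mL at entry and r the rate in the others. Neither is in the documents. I assume f = 10, 20 or 30% and r = 30%, and that every entrant below 100 still qualifies at Week 24 (an upper bound). The reported rate is f + (1 − f)r:
- 0.10 + 0.90 × 0.30 = 0.37
- 0.20 + 0.80 × 0.30 = 0.44
- 0.30 + 0.70 × 0.30 = 0.51

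The excess over r is f(1 − r) = 7, 14 or 21 points. If treatment did nothing (r = 0), the reported rate would be about f. In whole participants, 3/34 = 8.8% (90% Clopper-Pearson CI 2.4 to 21.3), 7/34 = 20.6% (10.1 to 35.2) and 10/34 = 29.4% (16.9 to 44.8).

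**4. Dilution between arms.** With f equal across arms, the observed difference is (1 − f) times the true one. A 30-point difference becomes 0.9 × 30 = 27, 0.8 × 30 = 24 or 0.7 × 30 = 21 points. Taking 50% versus 80% among the others, 34 per arm and one-sided 0.05 without multiplicity adjustment, power falls from 84% to 78, 72 or 65%.

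**5. Chance imbalance.** Ignoring stratification, the SD of the difference in f between two arms is √(2f(1 − f)/34) = 7.3, 9.7 or 11.1 points. This is an upper limit, because everyone below 100 lies within the <1,000 IU/mL randomization stratum. If half of participants were below 1,000 (an assumption), √(2f(1 − 2f)/34) gives about 6.9, 8.4 and 8.4. An imbalance reaches the between-arm difference multiplied by 1 − r = 0.7, so the upper limits become 5.1, 6.8 and 7.8 points.

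**The case against.** Several points on the other side stand.

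- **The primary endpoint is sound.** A reader might infer that the main Week 24 result credits entry status. It does not: it requires a decline of at least 2 log10 from baseline, and the amendment summary says it was adjusted to accommodate the new entry limit. HBsAg change, decline cut-offs and a repeated-measures model are also planned.
- **No systematic bias between arms.** A reader might infer that one arm is favoured on the completion rate. Randomization keeps f equal in expectation, so the systematic effect is dilution and only chance imbalance is left.
- **Not every low entrant counts as a success.** HBV DNA of 20–59 IU/mL can pass entry and fail completion. ALT must also be <3x ULN at Week 24, and Protocol 2.3.2.2.1 reports ALT flares in 7% of REEF-1 participants on JNJ-3989 200 mg every 4 weeks. The figures above are therefore upper bounds.
- **Some of this will be visible.** SAP Table 12 tabulates baseline HBsAg <100 and Table 8 lists it as an efficacy subgroup. Section 5.4.2.1 allows displays by subgroup and exploratory logistic models, and 5.4.2.3 plans Cox models with selected baseline factors. None of these commits to a split for the two outputs at issue.
- **The outputs are not confirmatory.** The completion rate is a secondary endpoint without multiplicity control, and time to HBsAg <100 is an addition made in the SAP.
- **Lack of an NA-stop control affects every completer.** It applies at any baseline HBsAg, and splitting at 100 IU/mL does not supply one.

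**Conclusion.** The gap is real and should be closed. As written, the end-of-treatment completion rate mixes what treatment achieved with what was present at entry, and time to HBsAg <100 includes participants who were never at risk. The SAP already handles this for HBV RNA, HBcrAg and ALT normalization, so the omission for HBsAg <100 is also out of line with its own practice.

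That some entrants can qualify on Day 1 follows directly from the criteria. The size is not established, since f and r are both assumed. Under those assumptions the per-arm rate is raised by up to 7 to 21 points over the rate in the others. That excess is smaller than the 10 to 30 points already qualifying at entry and should not be read as that share. A true 30-point difference shrinks to between 27 and 21 points. The documents do not support extending the criticism to the primary test or its type I error.

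**What to change.** 1. **SAP 5.4.1.3.1:** restrict time to first HBsAg <100 IU/mL to participants with baseline HBsAg of at least 100 IU/mL, in line with HBV RNA and HBcrAg. This removes events fixed by entry status. A remaining Week 2 versus Week 4 difference in detection for early responders should be acknowledged.
2. **SAP 5.4.2.1.2:** keep the protocol-defined proportion on all FAS participants. Add the proportion meeting the criteria at baseline, by arm, taking screening as the previous HBV DNA value. Commit to a Week 24 (or FU Week 2) analysis among participants not meeting the criteria at baseline, and interpret treatment effect from it. Define that group by the full criteria and not by HBsAg alone, because an entrant below 100 with HBV DNA of 20–59 IU/mL may not qualify at baseline.
3. **Off-treatment results:** present FU Week 24 and 48 seroclearance and HBV DNA results in NA completers split at baseline HBsAg 100 IU/mL, and say that this does not replace an NA-stop control.

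The cost is SAP wording and a few tables. No new data are needed, and the clinical stopping rule is unchanged. The price is a smaller denominator, about 34 × 0.9 = 31 down to 34 × 0.7 = 24 per arm under the assumed shares, and a less favourable proportion.

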3. OBJECTIVES AND ENDPOINTS

Below is the list of objectives and endpoints that will be evaluated in this study, delineating the details in alignment with the general objectives listed in the Master Protocol PLATFORMPAHPB2001. The details specific for this ISA are highlighted (colored fill).

Objectives	Endpoints
Primary	

 To evaluate the efficacy in terms of HBsAg changes from baseline for the treatment regimens of 24 weeks of JNJ-3989 + 24 weeks of NA + 12 or 24 weeks of PegIFN-α2a (with immediate or delayed start of PegIFN-α2a treatment), as compared to NA standard of care treatment. 	
 Proportion of participants with a reduction of at least 2 log₁₀ IU/mL in HBsAg levels from baseline at Week 24 (EOSI).
Secondary	

 To evaluate the safety and tolerability of the study intervention. 	
 Safety and tolerability including but not limited to the proportion of participants with (S)AEs and abnormalities in clinical laboratory tests (including hematology, blood biochemistry, blood coagulation, urinalysis, urine chemistry, renal biomarkers), 12-lead ECGs, vital signs, and ophthalmologic and physical examinations throughout the study.

 To evaluate the efficacy of the study intervention at the end of the 24-week treatment period. 	
 Proportion of participants meeting the protocol-defined NA treatment completion criteria based on the Week 24 (EOSI) or FU Week 2 results.

 To evaluate the efficacy of the study intervention during the FU period in those participants who met the protocol-defined NA treatment completion criteria based on the Week 24 or FU Week 2 results. 	
 Proportion of participants with HBsAg seroclearance at FU Week 24 and 48 (ie, 24 and 48 weeks after completion of all study interventions at Week 24) without re-starting NA treatment. Proportion of participants with HBV DNA <LLOQ at FU Week 24 and 48 (ie, 24 and 48 weeks after completion of all study interventions at Week 24) without re-starting NA treatment. Frequency of virologic and/or biochemical flares. Proportion of participants requiring NA re-treatment.

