4.3. Justification for Dose and Treatment Duration

The proposed dose and treatment duration for JNJ-3989 are selected to maximize the chance for patients to achieve functional cure and are supported by scientific understanding of available data. The same dose (ie, 200 mg of JNJ-3989) is currently being tested in ongoing Phase 2b studies REEF-1 (73763989HPB2001), REEF-2 (73763989PAHPB2002), REEF-IT (73763989PAHPB2005), and Penguin (73763989PAHPB2006). Addition of short-term PegIFN- α 2a (12 or 24 weeks, with immediate or delayed start) to the treatment regimen is expected to enhance antiviral activity of JNJ-3989 + NA and may lead to a shorter overall treatment duration (ie, 24 weeks) needed to achieve functional cure.

Clinical data on PK, PD, safety, and efficacy of JNJ-3989 are available from the Phase 1/2a AROHBV1001 study. The study has been completed and the final study report is available. Twenty adult healthy participants have received single subcutaneous injections of JNJ-3989 (35, 100, 200, 300, and 400 mg) and 84 adult chronic HBV-infected participants have received multiple doses of JNJ-3989 (25, 50, 100, 200, 300, and 400 mg), administered as 3 subcutaneous injections separated by either 7-day, 14-day, or 28-day intervals. All participants either continued or started on ETV or tenofovir disoproxil on Day 1.

JNJ-3989 was generally safe and well tolerated at all doses. No clinically relevant safety signal was identified.

Antiviral activity data were available for 56 chronic HBV-infected participants who received 3 subcutaneous injections of 25 to 400 mg JNJ-3989 Q4W (Gane 2019; Yuen 2019; IB JNJ-3989). In general, mean HBsAg declines reached nadir at Day 113 (ie, 8 weeks after last JNJ-3989). Mean HBsAg levels remained suppressed (below baseline levels) at least until Day 392 (ie, 9 months after last dose) in a substantial proportion of patients. The HBsAg levels at Day 392 were variable with some patients having HBsAg levels close to baseline levels while a substantial proportion of

patients still had HBsAg levels $>1 \log_{10}$ IU/mL lower than the baseline levels. JNJ-3989 showed activity on other viral markers (HBV DNA, HBV RNA, HBeAg and HBcrAg), frequently with sustained reduction at least until Day 362. No apparent dose response was observed at doses between 100 mg and 400 mg JNJ-3989, a numerically smaller mean decline was observed at the lower doses of 25 mg and 50 mg, mainly apparent after end of JNJ-3989 dosing.

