### 1.1. Objectives and Endpoints

Objectives	Endpoints
Primary	

 
To evaluate the efficacy in terms of HBsAg changes from baseline for the treatment regimens of 24 weeks of JNJ-3989 + 24 weeks of NA + 12 or 24 weeks of PegIFN-<math>\alpha</math>2a (with immediate or delayed start of PegIFN-<math>\alpha</math>2a treatment), as compared to NA standard of care treatment.
 
	
 
Proportion of participants with a reduction of at least 2 log10 in HBsAg levels from baseline at Week 24 (EOSI).
 

Secondary	

 
To evaluate the safety and tolerability of the study intervention.
 
	
 
Safety and tolerability including but not limited to the proportion of participants with (S)AEs and abnormalities in clinical laboratory tests (including hematology, blood biochemistry, blood coagulation, urinalysis, urine chemistry, renal biomarkers), 12-lead ECGs, vital signs, and ophthalmologic and physical examinations throughout the study.
 

 
To evaluate the efficacy of the study intervention at the end of the 24-week treatment period.
 
	
 
Proportion of participants meeting the protocol-defined NA treatment completion criteria at Week 24 (EOSI) or FU Week 2 results.
 

 
To evaluate the efficacy of the study intervention during the FU period in those participants who meet the protocol-defined NA treatment completion criteria based on the Week 24 or FU Week 2 results.
 
	
 
Proportion of participants with HBsAg seroclearance at FU Week 24 and 48 (ie, 24 and 48 weeks after completion of all study interventions at Week 24) without re-starting NA treatment.
 

Objectives	Endpoints
	
 
Proportion of participants with HBV DNA <LLOQ at FU Week 24 and 48 (ie, 24 and 48 weeks after completion of all study interventions at Week 24) without re-starting NA treatment.
 
Frequency of virologic and/or biochemical flares.
 
Proportion of participants requiring NA re-treatment.
 

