## **5.4.1. Definitions**

### **5.4.1.1. Binary Endpoints**

#### **5.4.1.1.1. NA Treatment Completion Criteria**

NA treatment completion criteria are defined based on the Week 24 results as follows:

- ALT <3x ULN, and
- HBV DNA <60 IU/mL at Week 24 and HBV DNA<LLOQ at the previous visit, or HBV DNA< LLOQ at Week 24, and
- HBeAg-negative, and
- HBsAg <100 IU/mL

*Note:* Participants who are close to meeting the protocol-defined NA treatment completion criteria with the Week 24 results, and do meet the criteria based on the FU Week 2 results may be allowed to stop NA at FU Week 4, after consultation with the Sponsor. In case of ALT elevation  $\geq 3x$  ULN at Week 24, the investigator must consider different potential causes of increased ALT to ensure appropriate work up and management as needed. If the ALT elevation is unrelated to HBV activity and/or <3x ULN by FU Week 2, NA completion may be considered at the discretion of the investigator and in consultation with the sponsor.

The NA completion criteria will be assessed based on clinical laboratory tests and summarized based on the Week 24 (EOSI) or FU Week 2 results, and during the FU phase.

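### SAP 5.4.2.1.2 does not tabulate the secondary endpoint as defined: NA completion criteria met on Week 24 or FU Week 2 results

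*SAP*

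**What the plan says.** Section 3 of the protocol sets as a secondary endpoint the proportion of participants "meeting the protocol-defined NA treatment completion criteria based on the Week 24 (EOSI) or FU Week 2 results". SAP 1.1 lists the same endpoint, slightly reworded: "Proportion of participants meeting the protocol-defined NA treatment completion criteria at Week 24 (EOSI) or FU Week 2 results".

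Two visits count because NA can be stopped on either. Under Protocol 6.5.1, a participant who meets all four criteria on the Week 24 results stops NA at FU Week 2. One who was close at Week 24 and meets them on the FU Week 2 results may stop at FU Week 4, after consultation with the sponsor.

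SAP 5.4.1.1.1 opens with Week 24 only: "NA treatment completion criteria are defined based on the Week 24 results as follows". It then adds the FU Week 2 route in a note and closes by saying that the criteria will be "summarized based on the Week 24 (EOSI) or FU Week 2 results, and during the FU phase".

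The matching methods section, SAP 5.4.2.1.2, specifies three summaries by arm:

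1. the count and proportion, with 90% CI, of participants "who met the NA treatment completion criteria at Week 24, will be summarized by intervention arm";
2. from the end of treatment onward, participants "who did not meet the NA treatment completion criteria will be summarized at each timepoint during the study by intervention arm", with the criteria that failed;
3. the count and proportion, with 90% CI, meeting the criteria at any point in the FU phase.

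SAP Appendix 2 (6.2) declares no departure from the protocol's planned analyses.

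**The concern.** The definition names one quantity and the methods name three others. Someone programming from 5.4.2.1.2 would produce a Week 24 row, and that row is the one most likely to be reported as the endpoint. A participant who qualified only at FU Week 2 would then be scored as not meeting it, although the protocol allows that person to stop NA. The protocol expects such cases: 6.5.1 discusses ALT that is at or above 3x ULN at Week 24 and below it by FU Week 2.

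The third summary answers a different question. It includes participants who first qualify after FU Week 2, whom 6.5.1 keeps on NA. Late qualifiers are plausible. Protocol 4.3 reports that in the Phase 1/2a study "mean HBsAg declines reached nadir at Day 113", eight weeks after the last JNJ-3989 injection, so HBsAg could first fall below 100 IU/mL after FU Week 2. That study gave three injections without PegIFN, so it shows the possibility and gives no rate for this regimen.

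The choice of flag also matters downstream. The follow-up objective is restricted to participants who met the criteria on Week 24 or FU Week 2 results. SAP 5.1.6 defines the NA reference timepoint only for those who met them at end of treatment (EOT), which leaves out FU Week 2 qualifiers who may stop NA at FU Week 4. SAP 5.4.1.3.3 and 5.4.2.1.14 say only that the criteria were met, without saying on which results.

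**Working it through.** The documents give no rate, power or sample size for this endpoint, so there is no stated figure to reproduce. The check is set logic, followed by an illustration with assumed counts.

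**Inputs.** 34 participants per arm (Protocol 9.2, SAP 3); two-sided 90% Clopper-Pearson intervals (SAP 5.1.5); phase boundaries (SAP Table 3); visit windows (SAP Table 4).

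Within one arm, let A be the participants who meet the criteria on Week 24 results, B those who meet them on FU Week 2 results, and C those who meet them at any visit in the FU phase. The endpoint is |A ∪ B| / 34.

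**Step 1: the Week 24 row.** This is |A| / 34. Since A ⊆ A ∪ B, it can only equal or fall below the endpoint. The shortfall is k/34, where k is the number in B but not in A: 1/34 = 2.9 points, 3/34 = 8.8 points, 5/34 = 14.7 points. With an assumed 14 of 34 meeting the criteria at Week 24:

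| k (assumed) | Week 24 row | Endpoint | 90% CI of endpoint | Shortfall (points) |
|---|---|---|---|---|
| 0 | 41.2% | 14/34 = 41.2% | 26.9 to 56.7 | 0 |
| 1 | 41.2% | 15/34 = 44.1% | 29.5 to 59.5 | 2.9 |
| 3 | 41.2% | 17/34 = 50.0% | 34.9 to 65.1 | 8.8 |
| 5 | 41.2% | 19/34 = 55.9% | 40.5 to 70.5 | 14.7 |

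**Step 2: the by-timepoint table.** With complete data this gives 34 − |A| and 34 − |B|. Those two margins do not fix the union, which can lie anywhere from max(|A|, |B|) to min(34, |A| + |B|). With an assumed 14 qualifying at each visit, the endpoint could be from 14/34 = 41.2% to 28/34 = 82.4%.

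**Step 3: the any-time-in-FU row.** This is |C| / 34. Table 3 ends the treatment period one day before the Week 24 study agent intake and starts FU the next day. Read literally, a sample drawn on the Week 24 dosing day falls on FU Day 1, inside the window that Table 4 gives to FU Week 2 (days 1 to 22).

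- If Week 24 samples count as FU, C contains A ∪ B and the row can only equal or exceed the endpoint.
- If they do not, C contains B but not necessarily A. A participant who qualified at Week 24 and at no later visit is missed, and the row can fall on either side of the endpoint.

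Under neither reading is it the endpoint.

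**Step 4: by arm.** The last PegIFN dose is at Week 23 in Arms 1 and 2 and at Week 11 in Arm 3 (Protocol 6.5.1). Protocol 2.3.2.1 describes transient ALT rises and says that such disorders often, but not always, resolve once PegIFN stops. It gives no time frame. So k could be larger in Arms 1 and 2, but the documents contain no rate by arm from which to calculate a difference.

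**The case against.** The strongest reply is that the SAP has not dropped the endpoint. Sections 1.1 and 5.4.1.1.1 both retain it, and 5.4.1.1.1 promises a summary on that basis. This stands: the fault is a gap between definition and methods within the SAP. It does not close the gap, because the methods section is what specifies the tables.

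Second, the by-timepoint table covers FU Week 2 and shows which criteria failed, so an ALT-driven failure at Week 24 would be visible by arm. That also stands. The table still does not give the union (Step 2), and no CI is specified for it.

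Third, a reader might infer that the SAP overcounts the endpoint through the any-time-in-FU row. The documents do not support this. The row is not presented as the endpoint; it matches the separate reference to the FU phase at the end of 5.4.1.1.1, and it need not exceed the endpoint (Step 3).

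Fourth, a reader might infer that the any-time flag defines the follow-up population. Nothing in the SAP says so. The restricted denominators in 5.4.2.1.5.2 and 5.4.2.1.10 rest on having stopped all interventions, including NA, and not having restarted NA. The real downstream weakness is narrower: 5.1.6 uses EOT alone, and two other sections do not say which results count.

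**Conclusion.** Wrong as written, but minor. The methods in SAP 5.4.2.1.2 do not estimate the secondary endpoint that the protocol and the SAP both define. The Week 24 row can only equal or understate it, by 2.9 points per FU Week 2 qualifier in an arm of 34. That figure assumes the planned arm size. The number of such participants is unknown and may be zero, so an understatement is possible but not demonstrated.

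A reader might go further and conclude that the shortfall biases the comparison of arms. The different PegIFN end dates make that possible, but any figure for it would rest on invented counts. ALT flares are also not confined to PegIFN: Protocol 2.3.2.2.1 reports them in 7% of participants on JNJ-3989 200 mg every 4 weeks in REEF-1, and all three arms here receive that dose.

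The consequence is limited because this endpoint is reported with 90% CIs and no multiplicity adjustment (SAP 5.1.7). The primary test does not use it.

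**What to change.** In SAP 5.4.2.1.2:

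- Make the main row the count, proportion and 90% CI, by arm, of participants who meet all four criteria on the Week 24 results or, if not, on the FU Week 2 results. Show the two components separately.
- Keep the by-timepoint table. Label the any-time-in-FU summary as additional and descriptive.
- State which analysis phase holds the Week 24 sample, given the boundaries in Table 3.

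Elsewhere in the SAP, use the same Week 24 or FU Week 2 flag wherever an analysis is restricted to participants who met the criteria: the NA reference timepoint (5.1.6), time to HBV DNA below LLOQ (5.4.1.3.3) and the additional off-treatment flare analysis (5.4.2.1.14).

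The cost is a few lines of SAP text and one derived variable. No new data are needed, since Protocol 6.5.1 already has the criteria assessed on FU Week 2 results.
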